#### COMIRB Protocol

COLORADO MULTIPLE INSTITUTIONAL REVIEW BOARD [name] [contact] [contact]

Protocol #: 17-1042

 Project Title: Randomized interventiOn of Biventricular pacemaker function on ventricular function among patients with mechaNical circulatory support devices: "ROBIN"

 Principal Investigator:
 [name] [name]

 Version Date: 4/24/2019

I. Hypotheses and Specific Aims:

- Specific Aim 1: Determine how cardiac-resynchronization therapy (CRT) influences ventricular performance at rest and during activity/exercise in patients with CF-LVADs. Hypothesis 1: Cardiac output (Qc) and functional capacity are higher with CRT-pacing enabled, as opposed to conventional treatment with CRT-pacing disabled.
- Specific Aim 2: Determine how the right ventricle (RV) functions at rest and during exercise among patients with CF-LVADs. Hypothesis 2A: During resting conditions, adjustments of the CF-LVAD pump speed will alter venous return of blood to the heart, causing RV workload to increase and decrease in response to increases and decreases in pump speed, respectively. Hypothesis 2B: During exercise, progressive increases in venous return will increase RV workload and limit the patient's ability to exercise.

# II. Background and Significance:

**Heart failure (HF) is a devastating disease that affects 6 million people in the United States alone.** Overall 5-year survival of patients with HF is only 50% and there are significant reductions in quality of life (QOL). While beta-blockers and angiotensin-converting-enzyme inhibitors (medications considered "standard of care") have led to improvements in outcomes, many patients progress to end-stage, advanced HF, which has an even higher 5-year mortality rate of 80%. While heart transplantation is considered the gold-standard treatment for advanced HF, only ~2,000 donor organs are available per year. As such, demand for a definitive treatment of advanced HF far outweighs supply of available donor organs. To remedy this disparity, continuous-flow (CF) left ventricular assist devices (LVADs), so called "mechanical hearts", have emerged as an attractive alternative. Over 10,000 devices have been implanted over the past decade since CF-LVADs were incorporated into clinical practice, and almost 2,500 implanted in 2013 alone. CF-LVADs restore cardiac output (Qc) to normal levels through a rotating impellar that propels blood from the left ventricle into the ascending aorta. Total Qc therefore is determined by: 1) the CF-LVAD, which provides the bulk of flow to the body, at least during resting conditions; and 2) the heart, which can still provide small amounts of flow to the body by the expulsion of blood through the aortic valve as the heart contracts

Unfortunately, HF-related symptoms and functional impairments persist after insertion of a CF-LVAD.

[figure not shown]
While survival and QOL generally improve following CF-LVAD implantation, functional limitations and impairments in exercise capacity persist despite the return of resting Qc to normal levels. Device-related complications are a major source of morbidity. However, post-implantation HF is common, with almost half of patients reporting significant limitations in function 6-12 months after device insertion. The average six-minute hall walk score (6MHW, ~350m) and peak oxygen uptake (VO2, 12ml/kg/min) remain low 6-12 months following device implantation compared to normal levels in healthy individuals (normal 6MHW ~600±90m^23, average age-matched peak VO2 ~25-30ml/kg/min). Importantly, cardiovascular-related mortality rises exponentially for patients with 6MHW less than 345m^25 and VO2 less than 14ml/kg/min. Finally, despite a 1-year post-implantation survival rate of ~80%, survival at four years remains low at less than 50%. Thus, despite the assistance to the heart that the device provides, relief from HF-related symptoms is incomplete, which increases the risk of morbidity and mortality over time and is a major limitation of these devices.

**RV** performance during exercise, even among healthy individuals, is incompletely understood and poorly described among patients with CF-LVADs. Ventricular function is best characterized by formation of pressure-volume (PV) loops, which characterize ventricular performance during all phases of the cardiac cycle (figure 1). Based on animal models, the RV has been found to be a highly compliant, low-pressure chamber (especially compared to the muscular left ventricle (LV). In humans, *noninvasive methods* (e.g. echo) have been used to *estimate* how the RV responds to increases in venous return among healthy individuals that occur with exercise. Using high-fidelity conductance (Millar) catheters, it has been shown that diastolic stiffness increases among patients with coronary artery disease and/or hypertension), possibly as a result of ischemia or pericardial constraint. However, RV performance – throughout the *entirety* of the cardiac cycle, during exercise *among healthy individuals* – has not been fully characterized. However, this information can be obtained through use of these high-fidelity conductance catheters (Millar). Thus, there is a need (and the ability) for further investigation of the body's response to changes in loading conditions (such as occurs during exercise), in this population. This information is useful to further understand how the body responds to the hemodynamic demands of exercise, and also will serve as a platform for future investigations to define "normal" responses that diseased populations can be compared to.

**CF-LVAD implantation may compromise RV function.** The LVAD functions by continuous rotation of a rotor, which creates a suction effect and pulls oxygenated blood into the device, which is then propelled forward to the body. However, this suction also pulls the interventricular septum away from the RV, which increases the diameter of the RV and increases RV wall stress according to the Law of Laplace (wall stress is proportional to the radius of the ventricle). With the onset of activity, there is increased venous return of blood to the RV, and a compromised RV may be unable to accommodate this increase in bloodflow. As such, RV function may impair exercise capacity. It is unclear why VO2 and 6MWD scores (as detailed above) remain so low, and the primary determinants of exercise capacity among CF-LVAD patients are not clearly defined.

Following CF-LVAD implantation, there is little data available to guide clinicians with respect to cardiac resynchronization therapy pacemaker-defibrillator (CRT-D) settings. In the setting of advanced HF, CRT-D devices are implanted into individuals with underlying left bundle branch block (LBBB) conduction abnormalities. A LBBB causes "dyssynchrony" between the right (RV) and left ventricles (LV), meaning that they no longer contract at the same time. A CRT-D device is implanted in these patients and includes a coronary sinus (CS) lead on the left side of the heart, in addition to standard pacing/defibrillator leads, which are positioned on the right side of the heart. With pacing leads positioned on both sides of the heart, the CRT-D can pace both ventricles simultaneously, effectively resolving the LBBB conduction abnormality. However, following CF-LVAD implantation, the CRT-D device is left in place, but optimal device settings are unknown – specifically, it is unclear whether the CS lead should remain activated or deactivated. In the absence of

definitive data, conventional management is to deactivate the CS-lead. This strategy theoretically allows the interventricular septum to contribute to RV function at the expense of the LV (ie, the septum contributes more to RV function and less to LV function; since the LV is supported by the LVAD, this strategy theoretically should not compromise systemic perfusion). However, my preliminary data suggest the opposite - namely, that cardiac output (Qc), improves with the CS-lead enabled. Confirmation of these findings, along with a comprehensive analysis of the impact of CRT pacing on ventricular function and cardiac performance at rest and activity/exercise, will fill current gaps in knowledge about the interaction between

Protocol Template CF-146, Effective 7/10/11

CF-LVADs and CRT-D devices and provide the community with information about best-practices to optimize cardiovascular function and improve exercise capacity in these patients.

# **IV. Research Methods:**

# A. Outcome Measure(s):

**For specific Aim 1:** The primary outcome will be the difference in Qc (inert rebreathing) and peak VO2 between CS-lead ON v. OFF. Secondary measures include vital signs including HR and BP, as well as 6-minute hall walk test, 10 minute gait speed test, and quality of life measures (Kansas City Cardiomyopathy Questionnaire and Minnesota Living with Heart Failure Questionnaire), all compared between CS-lead ON v. OFF.

**For Specific Aim 2:** The primary outcome will be the pressure-volume (PV) area as measured by Millar catheterization – this data variable is a direct marker of "how hard" the RV must work in the face of changes in preload (venous return). Secondary outcomes include: end-systolic pressure volume relationship (ESPVR), which assesses changes in contractility, end-diastolic pressure volume relationship (EDPVR), which assesses ventricular compliance during the diastolic portion of the cardiac cycle, dp/dt (increase in ventricular pressure during isovolemic contraction period), and tau (measure of isovolemic relaxation of the ventricle). All of these variables will be assessed during changes in LVAD pump speed, and during exercise testing (on visits 1-2, see figure 2 below) with CS-lead ON v. OFF.

- B. Description of Population to be Enrolled for completion of specific aims 1-2:
- 15 patients with advanced HF who have already undergone CF-LVAD implantation. Inclusion criteria: 1) advanced HF patients who have already received CF-LVADs and are clinically stable, ambulatory outpatients and are fully recovered (at least 3 months) from LVAD implantationExclusion criteria: 1) individuals with clinical RV failure under resting conditions, defined as moderate-severely reduced RV systolic function on echocardiography, or clinical evidence of RV failure (elevated jugular venous pressures, 3 or 4+ [significant] peripheral edema); 2) disorders that adversely influence exercise ability (e.g. arthritis, peripheral vascular disease, pulmonary disease)
- 2. 13 healthy individuals will serve as a control group to define normal RV function during exercise. Healthy individuals will be defined as persons without a past medical history of cardiovascular disease or related disease (e.g. hypertension, diabetes, peripheral vascular disease, arrhythmias, stroke/transient ischemic attack) and are not taking any cardiac-related medications (e.g. antihypertensive medications). Potential subjects will be recruited by posting flyers at the University of Colorado Anschutz Medical Campus. Individuals requiring systemic anticoagulation with vitamin-K antagonists or new/direct oral anticoagulants ("NOAC"/"DOAC") will not be considered for study. Exclusion criteria for this control group includes: 1) individuals requiring systemic anticoagulation with

vitamin-K antagonists or new/direct oral anticoagulants ("NOAC"/"DOAC"); 2) disorders that adversely influence exercise ability (e.g. arthritis, peripheral vascular disease).

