## E. Potential Scientific Problems:

1)Recruitment of subjects for testing: The University of Colorado has an active heart failure and LVAD program, with approximately 50 CF-LVADs inserted in 2015 and over 70 patients followed in the advanced heart failure center. There are currently 37 CF-LVAD patients with CRT-D devices that are being followed clinically by the advanced heart failure and electrophysiology programs here at the University of Colorado. Thus, we do not anticipate any difficulty recruiting subjects for this proposal. Healthy volunteers will be recruited by posting flyers around the University of Colorado Anschutz Medical Campus. We will plan to enroll 30 participants with the anticipation that there will be a few dropouts (no more than 5 anticipated).

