# G. Data Analysis Plan:

**For specific aim 1**, data across conditions among CF-LVAD patients (ie, CS-lead ON v. OFF) will be compared using repeated measures analysis of variance (ANOVA) with Bonferroni *post-hoc* tests for multiple comparisons. Linear mixed modeling with random effects will be used to account for the variability in hemodynamics (e.g. heart rate, blood pressure, cardiac output) that occur during pump speed adjustments and during progressive stages of exercise (rest, mild, moderate and peak exercise). Comparisons between healthy controls and CF-LVAD patients will be compared using the Mann Whitney U test. All statistical analyses will be

performed using a computer-based analysis system (SAS, V9.4, Cary NC, USA). A P value < 0.05 will be considered statistically significant.

**For specific aim 2**, data across conditions among CF-LVAD patients (CS-lead ON v. OFF) will be compared using a two-way repeated measures ANOVA, to determine the impact of CS-lead pacing and LVAD pump speed on RV performance, and the impact of CS-lead and exercise on RV performance, with Bonferroni *post-hoc* tests for multiple comparisons. Linear mixed modeling with random effects will be used to account for the variability in parameters of RV function (dp/dt, tau, ESPVR, EDPVR, and PV area). Comparisons between healthy controls and CF-LVAD patients will be compared using the Mann Whitney U test. All statistical analyses will be performed using a computer-based analysis system (SAS, V9.4, Cary NC, USA). A P value < 0.05 will be considered statistically significant.

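### The healthy control group has no age or sex criterion and is compared with LVAD patients by an unadjusted test, so this secondary comparison can be confounded by age and sex

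*Combined protocol and SAP*

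**What the plan says.** The population description in section IV.B gives the controls a defined role: "13 healthy individuals will serve as a control group to define normal RV function during exercise". Eligibility rests on medical history: "Healthy individuals will be defined as persons without a past medical history of cardiovascular disease or related disease". Cardiac medication, oral anticoagulation and conditions that limit exercise are also ruled out. Age and sex do not appear. Recruitment is by flyer: "Potential subjects will be recruited by posting flyers at the University of Colorado Anschutz Medical Campus". Section E (Potential Scientific Problems) repeats this: "Healthy volunteers will be recruited by posting flyers around the University of Colorado Anschutz Medical Campus".

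The comparison group is "15 patients with advanced HF who have already undergone CF-LVAD implantation".

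Section G (Data Analysis Plan) has the same sentence under both aims: "Comparisons between healthy controls and CF-LVAD patients will be compared using the Mann Whitney U test". The repeated-measures ANOVAs in that section are for CS-lead ON v. OFF within LVAD patients. The mixed models are described for variability across pump speeds, exercise stages and RV parameters, and no term for group, age or sex is named.

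Where the Background section benchmarks exercise capacity, it uses an age-specific norm: "average age-matched peak VO2 ~25-30ml/kg/min".

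**The concern.** A reference group is only as useful as its resemblance to the patients in everything except disease. Here nothing ties the two groups together on age or sex. Campus flyers combined with a rule of no cardiovascular history and no cardiac drugs may well draw younger volunteers. That is an inference, since the documents give no ages. The Background's norm shows that the protocol treats age as relevant to peak VO2.

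If the groups differ in age or sex, and the RV measures depend on either, the Mann-Whitney test will attribute that difference to patient status. The Background also wants the healthy data to serve as a definition of normal for later comparisons with diseased populations, so a skewed group would carry its bias forward. The controls undergo right heart catheterization and an arterial line to supply this reference. Matching cannot be added once they have been enrolled.

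A smaller gap lies in the same sentence of section G. Exercise has four stages, and patients with a CRT-D are tested at two visits. The plan does not say which stage, visit or CS setting supplies the single value per person that a Mann-Whitney test needs.

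**Working it through.** **The plan's own figure for controls.** The Power Analysis assumes a 50 msec fall in relaxation time from rest to exercise, SD about 20 msec, n = 10, alpha 0.05, and claims more than 90% power. For a paired t-test the noncentrality is (50/20) × √10 = 7.91 on 9 degrees of freedom, which gives power above 99.99%. If 20 msec is instead the SD of each measurement with no correlation, the SD of the change is 20 × √2 = 28.3 msec, the noncentrality is 5.59 and power is 99.85%. The claim is met either way. It concerns change within controls; no power is stated for LVAD v. control.

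**What a 15 v. 13 Mann-Whitney test can detect.** With relative efficiency 0.955 for normal data, the noncentrality for a difference of d SD is approximately d × √(0.955 × 15 × 13 / 28) = 2.58 d. With two-sided alpha 0.05 (the plan does not state sidedness), the detectable difference is about 1.13 SD at 80% power and 1.31 SD at 90%.

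**What a demographic shift alone would do.** Assume no true patient-v.-healthy difference, normal data, and a shift in the outcome due only to age and sex. Simulated rejection rates are below; ranges show the variation between runs.

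| Assumed shift (SD) | Share of comparisons with p<0.05 |
|---|---|
| 0 | about 5% |
| 0.25 | about 9% |
| 0.5 | 22–23% |
| 0.75 | 44–45% |
| 1.0 | about 68% |

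**What lies behind such a shift.** If age correlates r with the outcome and the groups differ by g SD of age, the shift is r × g. With r = 0.3 and age gaps of 0.5, 1, 1.5 and 2 SD, the unadjusted test rejects about 6%, 12%, 18% and 31% of the time. With r = 0.5 it rejects about 8%, 22%, 44% and 69%. A linear model with group and age stays at about 4–6% throughout. As the age gap goes from 0 to 2 SD, the standard error of the adjusted group difference rises from 0.37 to 0.53 SD (r = 0.3) or from 0.33 to 0.48 SD (r = 0.5). With 28 people, adjustment removes the bias but loses precision when the groups are far apart, so matching at recruitment is worth doing as well.

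**Which adjustment works for the exercise response.** Write the outcome for person i at stage s as group + stage + group-by-stage + b × age(i) + person effect + error. In the rest-to-peak change, b × age(i) and the person effect cancel. With complete data, age and sex main effects therefore do not adjust the group-by-stage contrast. If age acts on the change itself, the contrast is shifted by r × g, from 0.3 × 1 = 0.3 SD to 0.5 × 1.5 = 0.75 SD over the combinations tried. False rejection without an age term on the change ran from about 12–13% to 48%. With such a term it was about 5%.

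**The case against.** The strongest reply is that this comparison is secondary and largely descriptive. No hypothesis, primary outcome or power statement concerns LVAD v. control. Hypotheses 1, 2A and 2B and the outcomes in section IV.A are within-patient, and the controls' own power statement is rest v. exercise. That stands. It limits the reach of the point, but the plan still commits to a between-group significance test under both aims.

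It is also fair that the rejection rates are simply the test's power against shifts chosen for illustration. The age-specific norm in the Background is for peak VO2 and does not show that pressure-volume area or tau depends on age. Small shifts do little harm, as the 0.25 SD row shows.

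Four stronger readings are tempting, and the documents support none of them:

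- **That the trial's main results are confounded.** Patients are their own controls in the CS-lead, pump-speed and rest-to-exercise analyses.
- **That false positives are inflated by pooling stages or visits.** Nothing says that repeated values will be entered as if independent. Section G handles stages by repeated-measures and mixed models.
- **That a Mann-Whitney test cannot address the exercise response.** Applied to each person's rest-to-peak change, it can. The fault is that the value to be compared is not named.
- **That matching would isolate an LVAD effect.** Every LVAD patient also has advanced heart failure, and there is no heart failure group without an LVAD.

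**Conclusion.** The point holds for the LVAD v. healthy comparison only. Flyer recruitment, the absence of any age or sex criterion, and an unadjusted test as the only named between-group analysis are all in the text. Following the plan exactly could report an age or sex difference as a departure from normal RV response.

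Neither the size nor the direction of the bias can be computed from the documents. Over an assumed shift of 0.25 to 1.0 SD, the chance of a spurious p<0.05 runs from about 9% to 68%, against a nominal 5%. This rests on normal data, a two-sided test, 15 v. 13 complete observations and no true difference. The change is worth making because it is cheap and cannot be made after enrolment, not because the primary conclusions depend on it.

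**What to change.** 1. **Section IV.B, controls.** Recruit the same 13 controls to frequency-match the LVAD cohort on age band and sex. Report both distributions.
2. **Section G, value compared.** Name one value per person for the between-group test, for example the rest-to-peak change at visit 1. At visit 1 the LVAD group mixes CS-ON, CS-OFF and patients without a CRT-D, so say how CS setting is handled.
3. **Section G, adjustment.** Add an age- and sex-adjusted analysis of that change beside the Mann-Whitney test. If a mixed model with group-by-stage is used instead, include age-by-stage and sex-by-stage terms, because main effects alone leave the interaction unadjusted.
4. **Section H and reporting.** Describe the contrast as advanced heart failure with an LVAD v. healthy, not as an effect of the LVAD.

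Cost: slower recruitment if older volunteers are needed, a few degrees of freedom, and changes of wording. No participants or procedures are added.

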### Power Analysis:

For specific aim 1-2, based on pilot data, assuming an increase in resting Qc of 0.6Lmin following activation of CRT (coronary-sinus [CS] lead enabled [CS-ON], with a standard deviation of 0.2L/min, a sample size of 15 patients will provide greater than 90% power to detect a difference in Qc using an alpha of 0.05. Assuming an increase in right atrial pressure of ~15mmHg from rest to peak exercise (based on pilot data), a sample size of 15 patients will provide greater than 90% power to detect a difference in right atrial pressure of ~15mmHg from rest to peak exercise (based on pilot data), a sample size of 15 patients will provide greater than 90% power to detect a difference in right sided pressures from rest to peak exercise, using an alpha =0.05.

For healthy controls, based on available data previously described in the literature, assuming a reduction in RV relaxation time by 50msec from rest to exercise, a sample size of 10 patients will provide greater than 90% power to detect a difference in ventricular performance from rest to peak exercise, assuming a standard deviation of ~20msec and an alpha = 0.05.

### Study Design and Research Methods

An overview of the study protocol is displayed in figure 2. For completion of aim 1 (testing the effect of the coronary sinus [CS] lead on functional capacity. CF-LVAD patients who have a CRT-D device will complete visits 1-2 as detailed in figure 2 and in the protocol description below. For completion of aim 2, CF-LVAD patients who do not have a CRT-D will complete visit 1 only. For CF-LVAD patients with CRT-D, the study protocol will involve a double-blinded randomized crossover design. Immediately following enrollment, CF-LVAD subjects will be randomized in a double-blind, 1:1 fashion to cardiac pacing with the coronary sinus (CS) lead enabled or disabled (CS-ON v. CS-OFF). The pacing mode will be either VVI-R or DDD-R with a backup pacing rate set at 60bpm. After four weeks, patients will return for visit 1 testing. On completion of testing, cardiac pacing will be switched (CS-ON to CS-OFF, or vice-versa) for four weeks, following which patients will return for visit 2 testing, which is identical to visit 1 testing. In this manner, all subjects will complete testing with the CS-lead ON and the CS-lead OFF; subjects will serve as their own controls to determine the impact that CRT-D pacing has on cardiovascular function and exercise performance. Following completion of visit 2 testing, the study will be completed and original CRT-D device settings returned to baseline. Computerized randomization will be performed in a 1.1 ratio to a CS-lead ON v. OFF pacing strategy - this process will be completed and recorded by a study coordinator who does not have access to the data recorded throughout the study; neither the patient nor the PI will be aware of randomization status during testing. Pacemaker settings will be adjusted by an electrophysiologist who is part of the study group but does not have access to data being collected (to ensure that blinding is maintained).

Visits 1-2 will involve a baseline assessment of hemodynamics using a Swan-Ganz catheter, followed by invasive exercise testing with Millar catheters to provide a detailed analysis of ventricular function during exercise. The Swan-Ganz catheter is a 7-French flexible catheter that is routinely used for hemodynamic assessment for clinical and research purposes (we are currently using this catheter for COMIRB #16-1635). The purpose of this catheter is to determine baseline hemodynamic parameters (in "layman's terms", to describe pressures in the right and left sides of the heart, as well as the lungs), including cardiac output and pulmonary arterial saturation, which provides an assessment of the integrity of the cardiopulmonary system under resting conditions prior to exercise. The inclusion of Swan-Ganz catheter to determine resting hemodynamics will extend the protocol by only 5 minutes. NOTE: the Swan-Ganz catheter is quickly inserted and removed after pressures, cardiac output and pulmonary arterial saturation are obtained. The Millar catheter is a high fidelity, pigtail-shaped central-lumen. 7-French flexible catheter with pressure and conductance electrodes; the insertion technique is the same as that used for a standard right heart catheterization (for example, the same procedure used for IRB study #16-1635). These catheters allow for generation of pressure-volume (PV) loops, as well as several additional measures of ventricular function, including: 1) dp/dt (increase in ventricular pressure during isovolemic contraction period); 2) tau (measure of isovolemic relaxation of the ventricle); 3)end-systolic pressure volume relationship (ESPVR), which represents contractile function of the ventricle: 4) end-diastolic pressure volume relationship (EDPVR), which represents ventricular compliance; and 5) pressure-volume area, which represents the amount of mechanical energy generated from contraction of the ventricle. As such, these catheters provide several parameters that are

Protocol Template CF-146, Effective 7/10/11

essential to understand how CF-LVADs impact RV function, and also determine how RV function influences exercise capacity in these patients.

The testing protocol for visits 1-2 will involve two parts: Part A, and Part B, which will be completed following right heart catheterization. Part A involves LVAD pump speed adjustments at rest in the supine position. Part B involves submaximal and symptom-limited (maximal) exercise. Exercise will be performed using a stationary cycle ergometer. For Part A, measurements will include the following: HR, BP by arterial line, LVAD parameters (from LVAD monitor), pressure-volume loops from the Millar catheter and Qc (inert rebreathing). Echocardiography will be used during pump speed adjustments to assess parameters such as LV and RV systolic and end-diastolic volumes, septal position, and mitral/tricuspid regurgitant flow. For Part B, measurements obtained will include the following: HR, BP by arterial line, respiratory rate, Qc (inert rebreathing), LVAD parameters (flow, rotor speed, pulsatility index and power), echocardiography may be used to estimate flow through the LVAD and left ventricular outflow tract of the native heart), VO2, VCO2 by gas exchange, RPE and measurements outlined above from the Millar catheter (e.g. dp/dt, tau, ESPVR, EDPVR and pressure-volume area). A complete blood count (CBC) will be obtained at rest, prior to initiation of exercise. A CBC is necessary to obtain hemoglobin/hematocrit levels, which are used to further assess VO2 and other cardiac parameters (e.g. cardiac output). Notably, this blood sample will be obtained from the catheter that is placed for invasive hemodynamic monitoring - no additional catheters or peripheral IV's are required. Blood (venous and/or arterial) oxygen saturation levels will be drawn at rest and during each stage of exercise by removing a small amount of blood (approximately 1-2cc) from the catheters (arterial catheter will be used to check arterial oxygen saturation. Millar catheter will be used to check venous oxygen saturation level). Blood oxygen levels are necessary to determine oxygen consumption by exercising muscle. Cerebral and peripheral (musculoskeletal) oxygen uptake may be monitored noninvasively by NIRS. End-tidal carbon dioxide will be monitored by nasal capnography. Brain blood flow may be measured by transcranial Doppler ultrasonography.

On visits 1-2, additional testing will include: 1) echocardiography to measure parameters such as LV enddiastolic and systolic volumes, mitral regurgitation severity, and RV strain; 2) 6-minute hall walk and 10-meter walk test; 3) Kansas City Cardiomyopathy Questionnaire KCCQ) and Minnesota Living with Heart Failure Questionnaire (MLHFQ); 4) CRT-D device interrogation to assess for percentage of time that patients are paced by the CS lead, for ventricular and/or supraventricular arrhythmias, and any "therapies" delivered by the device, such as anti-tachycardia pacing or shocks for treatment of ventricular arrhythmias: and 5) a comprehensive medical history and physical exam.

Note that patients with CF-LVADs will complete two visits (visits 1-2); healthy controls will only complete one day of testing (visit 1) to define normal responses – healthy subjects will only complete part B (exercise testing); part A (pump speed adjustments) is not applicable to healthy controls, who do not have an LVAD.

